**CONFIDENTIAL**

205724

Efficacy: Figures						
StInt No.	SAC No.	Population	IDSL / Example Shell	Title	Programming Notes	Deliverable [Priority]
2.10		PP		Least Squares Mean (90% CI) Change from Baseline in E-RS: COPD Total Score at Month 6 by Baseline E-RS: COPD Total Score (<10, >=10)	One panel for each factor on the same page	StInt
2.11	2.10	PP		Least Squares Mean (90% CI) Change from Baseline in E-RS: COPD Total Score at Month 6 by Smoking Status at Screening (Current, Former)	One panel for each factor on the same page	StInt, SAC
2.12		PP		Least Squares Mean (90% CI) Change from Baseline in E-RS: COPD Total Score at Month 6 by Country	One panel for each factor, 4 panels per page	StInt
2.13	2.11	PP		Least Squares Mean (90% CI) Change from Baseline in E-RS: COPD Total Score at Month 6 by % Predicted FEV1 at Screening (<50, >=50)	One panel for each factor on the same page	StInt, SAC
2.14	2.12	PP		Least Squares Mean (90% CI) Change from Baseline in E-RS: COPD Total Score at Month 6 by Baseline CAT Score (<10, >=10)	One panel for each factor on the same page	StInt, SAC
2.15		PP		Least Squares Mean (90% CI) Change from Baseline in E-RS: COPD Total Score at Month 6 by Exacerbation History (>=2 moderate/severe vs. <2 moderate/severe, prior year)	One panel for each factor on the same page	StInt
2.16		PP		Least Squares Mean (90% CI) Change from Baseline in E-RS: COPD Total Score at Month 6 by COPD Medication Grouping at Baseline (ICS+LABA+LAMA, ICS+LABA, LABA+LAMA, Other)	One panel for each factor on the same page	StInt
2.17		PP		Least Squares Mean (90% CI) Change from Baseline in E-RS: COPD Total Score at Month 6 by CMH Status at Baseline	One panel for each factor on the same page	StInt

**CONFIDENTIAL**

205724

Efficacy: Figures						
StInt No.	SAC No.	Population	IDSL / Example Shell	Title	Programming Notes	Deliverable [Priority]
2.18		PP		Least Squares Mean (90% CI) Change from Baseline in E-RS: COPD Total Score at Month 6 by Season	All factors on one plot	StInt
	2.13	PP		Empirical Distribution Function Plot of E-RS: COPD Total Scores at Baseline	Total and subscale scores	Post SAC
	2.14	PP		Empirical Distribution Function Plot of E-RS: COPD Total Scores at Month 6	Total and subscale scores	Post SAC
Exacerbations						
2.19	2.15	PP		Median Rate Ratio (90% CrI) of On-treatment Moderate/Severe HCRU Exacerbations		StInt, SAC
2.20		ITT		Median Rate Ratio (90% CrI) of On-treatment Moderate/Severe HCRU Exacerbations		StInt
2.21	2.16	PP		Kaplan-Meier Plot of Time to First On-treatment Moderate/Severe HCRU Exacerbation		StInt, SAC
2.22	2.17	PP		Kaplan-Meier Plot of Time to First On-treatment Severe HCRU Exacerbation		StInt, SAC
EXACT Events						
	2.18	PP		Median Rate Ratio (90% CrI) of On-treatment EXACT Events		SAC
	2.19	PP		Kaplan-Meier Plot of Time to First On-treatment EXACT Event		SAC
SGRQ						
2.23	2.20	PP		Posterior Mean (90% CrI) Change from Baseline in SGRQ Total Score over Time		StInt, SAC
	2.21	PP		Mean (90% CI) SGRQ Total Score over Time	Baseline, Day 84 and 168	Post SAC

**CONFIDENTIAL**

205724

Efficacy: Figures						
StInt No.	SAC No.	Population	IDSL / Example Shell	Title	Programming Notes	Deliverable [Priority]
CAT						
2.24	2.22	PP		Posterior Mean (90% CrI) Change from Baseline in CAT Score over Time		StInt, SAC
	2.23	PP		Mean (90% CI) CAT Score over Time	Baseline, Day 84 and 168	Post SAC
2.25		PP		Least Squares Mean (90% CI) Change from Baseline in CAT Score at Month 6 by Baseline E-RS: COPD Total Score (<10, >=10)	One panel for each factor	StInt
2.26	2.24	PP		Least Squares Mean (90% CI) Change from Baseline in CAT Score at Month 6 by Smoking Status at Screening (Current, Former)	One panel for each factor	StInt, SAC
2.27		PP		Least Squares Mean (90% CI) Change from Baseline in CAT Score at Month 6 by Country	One panel for each factor	StInt
2.28	2.25	PP		Least Squares Mean (90% CI) Change from Baseline in CAT Score at Month 6 by % Predicted FEV1 at Screening (<50, >=50)	One panel for each factor	StInt, SAC
2.29	2.26	PP		Least Squares Mean (90% CI) Change from Baseline in CAT Score at Month 6 by Baseline CAT Score (<10, >=10)	One panel for each factor	StInt, SAC
2.30		PP		Least Squares Mean (90% CI) Change from Baseline in CAT Score at Month 6 by Exacerbation History (>=2 moderate/severe vs. 1 moderate/severe, prior year)	One panel for each factor	StInt

**CONFIDENTIAL**

205724

Efficacy: Figures						
StInt No.	SAC No.	Population	IDSL / Example Shell	Title	Programming Notes	Deliverable [Priority]
2.31		PP		Least Squares Mean (90% CI) Change from Baseline in CAT Score at Month 6 by COPD Medication Grouping at Baseline (ICS+LABA+LAMA, ICS+LABA, LABA+LAMA, Other)	One panel for each factor	StInt
2.32		PP		Least Squares Mean (90% CI) Change from Baseline in CAT Score at Month 6 by CMH Status at Baseline	One panel for each factor	StInt
2.33		PP		Least Squares Mean (90% CI) Change from Baseline in CAT Score at Month 6 by Season	All factors on one plot	StInt
Rescue Use						
	2.27	PP		Daily Mean Number of Puffs of Rescue Medication per Day using Diary Data over Time	Day -7 to Day 168	Post SAC
2.34	2.28	PP		Least Squares Mean (90% CI) Change from Baseline in Mean Number of Puffs of Rescue Use per Day using Diary Data over Time		StInt, SAC
2.35	2.29	PP		Least Squares Mean (90% CI) Change from Baseline in Percentage of Rescue-free Days using Diary Data over Time		StInt, SAC
	2.30	PP		Daily Mean Number of Occasions of Rescue Medication per Day using Sensor Data over Time	Day -7 to Day 168	Post SAC
	2.31	PP		Least Squares Mean (90% CI) Change from Baseline in Mean Number of Occasions of Rescue Use per Day using Sensor Data over Time		SAC
	2.32	PP		Least Squares Mean (90% CI) Change from Baseline in Percentage of Rescue-free Days using Sensor Data over Time		SAC

Efficacy: Figures						
StInt No.	SAC No.	Population	IDSL / Example Shell	Title	Programming Notes	Deliverable [Priority]
Conditional E-RS: COPD						
2.36-2.43	2.33-2.35	PP		Least Squares Mean (90% CI) Change from Baseline in E-RS: COPD Total Score over Time by Factor	Produced if an interaction between treatment and factor is significant at the 10% level Where Factor is defined in Section 7.3.1 One panel for each factor	StInt, SAC
Continue from above	Continue from above	PP		Least Squares Mean (90% CI) Change from Baseline in CAT Score over Time by Factor	Produced if an interaction between treatment and factor is significant at the 10% level Where Factor is defined in Section 7.3.1 One panel for each factor	StInt, SAC

14.11.7. Safety Tables

Safety: Tables						
StInt No.	SAC No.	Population	IDSL / Example Shell	Title	Programming Notes	Deliverable [Priority]
Adverse Events (AEs)						
3.1	3.1	mITT	AE1	Summary of On-treatment Adverse Events by System Organ Class and Preferred Term	ICH E3	StInt, SAC
3.2	3.2	mITT	AE3	Summary of Common (>=5%) On-treatment Adverse Events by Overall Frequency	ICH E3	StInt, SAC

Safety: Tables						
StInt No.	SAC No.	Population	IDSL / Example Shell	Title	Programming Notes	Deliverable [Priority]
3.3	3.3	mITT	AE1/AE3	Summary All On-treatment Drug-Related Adverse Events by [System Organ Class and] Preferred Term	ICH E3 Use AE1 for interim with text in [] in title Use AE3 for final reporting with text in [] omitted.	StInt, SAC
	3.4	mITT	AE15	Summary of Common (>=5%) Non-serious On-treatment Adverse Events by System Organ Class and Preferred Term (Number of Subject and Occurrences)	FDAAA, EudraCT	SAC
	3.5	mITT	AE1	Summary of Post-treatment Adverse Events		SAC
	3.6	ALLSUB	AE2	Relationship of Adverse Event System Organ Class, Preferred Term and Verbatim Text		SAC
	3.7	mITT	AE5A	Summary of All On-treatment Adverse Events by Maximum Intensity by System Organ Class and Preferred Term	ICH E3	SAC
	3.8	mITT	AE5A	Summary of On-treatment Drug-Related Adverse Events by Maximum Intensity by System Organ Class and Preferred Term	ICH E3	SAC
Serious and Other Significant Adverse Events						
	3.9	mITT	AE16	Summary of On-treatment Serious Adverse Events by System Organ Class and Preferred Term (Number of Subjects and Occurrences)	FDAAA, EudraCT	SAC
	3.10	ALLSUB	AE1/AE3	Summary of Pre-treatment Serious Adverse Events by [System Organ Class and] Preferred Term		SAC
3.4	3.11	mITT	AE1/AE3	Summary of On-treatment Serious Adverse Events by [System Organ Class and] Preferred Term	Use AE1 for interim with text in [] in title Use AE3 for final reporting with text in [] omitted.	StInt, SAC

Safety: Tables						
StInt No.	SAC No.	Population	IDSL / Example Shell	Title	Programming Notes	Deliverable [Priority]
3.5	3.12	mITT	AE1/AE3	Summary of On-treatment Fatal Serious Adverse Events by [System Organ Class and] Preferred Term	Use AE1 for interim with text in [] in title Use AE3 for final reporting with text in [] omitted.	StInt, SAC
3.6	3.13	mITT	AE1/AE3	Summary of On-treatment Adverse Events Leading to Permanent Discontinuation of Study Treatment or Withdrawal from Study by [System Organ Class and] Preferred Term	IDSL Use AE1 for interim with text in [] in title Use AE3 for final reporting with text in [] omitted.	StInt, SAC
3.7	3.14	mITT		Summary of On-treatment Adverse Events of Special Interest		StInt, SAC
	3.15	mITT		Summary of On-treatment Pneumonia (AE and SAE) by ICS	AE and SAE Subjects who have an event in the 'Infective pneumonia' SMQ By subjects receiving ICS for at least 7 days at the time on pneumonia onset.	Post SAC
Laboratory: Chemistry						
3.8	3.16	mITT	LB1	Summary of Chemistry Changes from Baseline	ICH E3, include change from baseline of min/max value	StInt, SAC
3.9	3.17	mITT	LB17	Summary of Worst Case Chemistry Results by Potential Clinical Importance Criteria	ICH E3	StInt, SAC
Laboratory: Hematology						
3.10	3.18	mITT	LB1	Summary of Hematology Changes from Baseline	ICH E3, include change from baseline of min/max value	StInt, SAC
3.11	3.19	mITT	LB17	Summary of Worst Case Hematology by Potential Clinical Importance Criteria	ICH E3	StInt, SAC

Safety: Tables						
StInt No.	SAC No.	Population	IDSL / Example Shell	Title	Programming Notes	Deliverable [Priority]
Laboratory: Hepatobiliary (Liver)						
3.12	3.20	mITT	LIVER1	Summary/Listing of Liver Monitoring/Stopping Event Reporting	IDSL – if there are very small number of events this summary will be replaced with a listing. Table title to be determined by content.	StInt, SAC
3.13	3.21	mITT	LIVER10	Summary/Listing of Hepatobiliary Laboratory Abnormalities	IDSL – if there are very small number of events this summary will be replaced with a listing. Table title to be determined by content.	StInt, SAC
ECG						
	3.22	mITT	EG1	Summary of ECG Findings	IDSL, include min/max value	SAC
	3.23	mITT	EG2	Summary of Change from Baseline in ECG Values by Visit	IDSL include change from baseline of min/max value	SAC
3.14	3.24	mITT	EG10	Summary of Maximum QTcF Values Post-Baseline Relative to Baseline by Category	IDSL	StInt, SAC
3.15	3.25	mITT	EG11	Summary of Maximum Increase in QTcF Values Post-Baseline Relative to Baseline by Category	IDSL	StInt, SAC
Vital Signs						
	3.26	mITT	VS1	Summary of Change from Baseline in Vital Signs	ICH E3, include change from baseline of min/max value	SAC
	3.27	mITT	VS7	Summary of Worst Case Vital Signs Results by Potential Clinical Importance Criteria	IDSL	SAC

Safety: Tables						
StInt No.	SAC No.	Population	IDSL / Example Shell	Title	Programming Notes	Deliverable [Priority]
Spirometry						
3.16	3.28	mITT		Summary of Baseline Post-Bronchodilator FEV1 (L)	Post bronchodilator FEV1 Include total column	StInt, SAC
3.17	3.29	mITT		Summary of Post-Bronchodilator FEV1 (L)	Post bronchodilator FEV1 Include raw and change from baseline	StInt, SAC
3.18	3.30	mITT		Analysis of Change from Baseline Post-Bronchodilator FEV1 (L) up to Month 6	Frequentist MMRM Endpoints: Post bronchodilator FEV1	StInt, SAC
3.19	3.31	mITT		Type III Tests of Fixed Effects for Analysis of Change from Baseline Post-Bronchodilator FEV1 (L)	Frequentist MMRM Endpoints: Post bronchodilator FEV1	StInt, SAC
3.20	3.32	mITT		Summary of Baseline Post-Bronchodilator FVC (L)	Post bronchodilator FVC Include total column	StInt, SAC
3.21	3.33	mITT		Summary of Post-Bronchodilator FVC (L)	Post bronchodilator FVC Include raw and change from baseline	StInt, SAC
3.22	3.34	mITT		Analysis of Change from Baseline Post-Bronchodilator FVC (L) up to Month 6	Frequentist MMRM Endpoints: Post bronchodilator FVC	StInt, SAC
3.23	3.35	mITT		Type III Tests of Fixed Effects for Analysis of Change from Baseline Post-Bronchodilator FVC (L)	Frequentist MMRM Endpoints: Post bronchodilator FVC	StInt, SAC
	3.36	mITT		Summary of Baseline Post-Bronchodilator FEV1/FVC	Post bronchodilator FEV1/FVC Include total column	Post SAC
	3.37	mITT		Summary of Post-Bronchodilator FEV1/FVC	Post bronchodilator FEV1 Include raw and change from baseline Day 84 and 168	Post SAC

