4. OBJECTIVES AND ENDPOINTS

Objectives	Endpoints

Primary
 
 • To characterize the dose response of danirixin compared with placebo on the incidence and severity of respiratory symptoms in participants with COPD • To compare the safety of danirixin with placebo in participants with COPD 	
 • Change from baseline in respiratory symptoms measured by E-RS:COPD daily diary at month 6: total score and subscales (i.e. breathlessness, cough and sputum, and chest symptoms) • Adverse events (AE), clinical laboratory values, vital signs, electrocardiogram (ECG)

Objectives	Endpoints

Secondary
 
 • To characterize the dose response of danirixin compared with placebo on the annual rate of moderate/severe COPD exacerbations in participants with COPD • To further characterize the clinical activity of danirixin compared to placebo in participants with COPD 	
 • Healthcare Resource Utilization (HCRU)-defined COPD exacerbations • E-RS:COPD Responder Analysis (including subscales) • Number of Exacerbations of Chronic Pulmonary Disease (EXACT) tool defined events • Time to first EXACT event • EXACT event severity • EXACT event duration for all events • Time to first HCRU-defined COPD exacerbation • Time to first severe HCRU-defined COPD exacerbation • HCRU-defined exacerbation duration • Change from baseline for the St. George's Respiratory Questionnaire (SGRQ) total score (derived from SGRQ-C) • SGRQ responder analysis • Change for baseline COPD Assessment Test (CAT) total score • CAT responder analysis • Lung function (FEV1, FEV1 % predicted, FVC, FEV1/FVC ratio) • Rescue medication use • Participant experience of physical activity (subset of approximately 50% of participants) measured using PROactive Clinic Visit Tool (C-PPAC)

Objectives	Endpoints

 To characterize the pharmacokinetics of danirixin in participants with COPD 	
 Danirixin concentration and standard pharmacokinetic parameters for danirixin (e.g. AUC, Cmax, Tmax), using dried blood spot data

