9.2.5. Cardiovascular and Death Events

For any cardiovascular events detailed in [Appendix 4](#) and all deaths, whether or not they are considered SAEs, specific Cardiovascular (CV) and Death sections of the CRF will be required to be completed. These sections include questions regarding cardiovascular (including sudden cardiac death) and non-cardiovascular death.

The CV CRFs are presented as queries in response to reporting of certain CV MedDRA terms. The CV information should be recorded in the specific cardiovascular section of the CRF within one week of receipt of a CV Event data query prompting its completion.

The Death CRF is provided immediately after the occurrence or outcome of death is reported. Initial and follow-up reports regarding death must be completed within one week of when the death is reported.

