9.2.6. Disease-Related Events and/or Disease-Related Outcomes Not Qualifying as SAEs

The following disease related events (DREs) are common in participants with COPD and can be serious/life threatening:

- COPD exacerbations

Because these events are typically associated with the disease under study, they will not be reported according to the standard process for expedited reporting of SAEs to GSK (even though the event may meet the definition of an SAE). These events will be recorded on the DRE page in the participant's CRF within 72 hours after the investigator becomes aware of the event. These DREs will be monitored by the Safety Review Team (SRT) on a routine basis as described in [Appendix 3](#).

NOTE: However, if either of the following conditions applies, then the event must be recorded and reported as an SAE (instead of a DRE):

- *The event is, in the investigator's opinion, of greater intensity, frequency, or duration than expected for the individual participant, or*
- *The investigator considers that there is a reasonable possibility that the event was related to treatment with the investigational product*

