- Any abnormal laboratory test results (hematology, clinical chemistry, or urinalysis) or other safety assessments (eg, ECG, radiological scans, vital signs measurements), including those that worsen from baseline, considered clinically significant in the medical and scientific judgment of the investigator (ie, not related to progression of underlying disease).
- Exacerbation of a chronic or intermittent pre-existing condition including either an increase in frequency and/or intensity of the condition.
- New conditions detected or diagnosed after study treatment administration even though it may have been present before the start of the study.
- Signs, symptoms, or the clinical sequelae of a suspected drug-drug interaction.
- Signs, symptoms, or the clinical sequelae of a suspected overdose of either study treatment or a concomitant medication. Overdose per se will not be reported as an AE/SAE unless it is an intentional overdose taken with possible suicidal/self-harming intent. Such overdoses should be reported regardless of sequelae.
- "Lack of efficacy" or "failure of expected pharmacological action" per se will not be reported as an AE or SAE. Such instances will be captured in the efficacy assessments. However, the signs, symptoms, and/or clinical sequelae resulting from lack of efficacy will be reported as AE or SAE if they fulfill the definition of an AE or SAE.

Events NOT Meeting the AE Definition

- Any clinically significant abnormal laboratory findings or other abnormal safety assessments which are associated with the underlying disease, unless judged by the investigator to be more severe than expected for the participant's condition.
- The disease/disorder being studied or expected progression, signs, or symptoms of

the disease/disorder being studied, unless more severe than expected for the participant's condition.

- Medical or surgical procedure (eg, endoscopy, appendectomy): the condition that leads to the procedure is the AE.
- Situations in which an untoward medical occurrence did not occur (social and/or convenience admission to a hospital).
- Anticipated day-to-day fluctuations of pre-existing disease(s) or condition(s) present or detected at the start of the study that do not worsen.

Definition of SAE

If an event is not an AE per definition above, then it cannot be an SAE even if serious conditions are met (eg, hospitalization for signs/symptoms of the disease under study, death due to progression of disease).

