
Season
 
 
• For each participant and each month, season will be assigned based on the first date with a non-missing daily score in the monthly mean E-RS: COPD total score.
 
• Australia will add 6 months to the first day of the monthly mean E-RS: COPD total score before season is assigned.
 
• If the month of the first day of the monthly mean score period is:             
 
▪ Dec, Jan or Feb then season is Winter
 
▪ Mar, Apr or May then season is Spring
 
▪ Jun, Jul or Aug then season is Summer
 
▪ Sep, Oct or Nov then season is Fall
 
 
 

Mean Number of Rescue Puffs per Day and Percentage Rescue Free Days
 
 
• If a participant has more than one daily diary record for any given day, the worst case response on that day for each endpoint will be used in the summaries and analyses. i.e. the maximum number of puffs of rescue use reported will be counted for the day in question and used to determine if it was a rescue-free day.
 
• A rescue-free day is defined as a day where the total puffs is 0.
 
• For each summary period, the mean number of puffs per day and the percentage of rescue free days, will be calculated, using the number of days with non-missing values for the endpoint as denominator.
 
• Rescue use will be summarized over the periods defined above.
 

HCRU Exacerbations
Duration

 
The duration of the exacerbation will be calculated as (exacerbation resolution date or date of death - exacerbation onset date + 1).
 

Severity

 
Each HCRU exacerbation will be categorized based on severity as follows:                             
 
Mild: no treatment with oral/systemic corticosteroids and/or antibiotics and not involving hospitalisation, an emergency room visit or resulting in death
 
Moderate: required treatment with oral/systemic corticosteroids and/or antibiotics (not involving hospitalisation, an emergency room visit or resulting in death).
 
Severe: required in-patient hospitalization, an emergency room visit, or resulted in death
 
 
 

Time to First Exacerbation

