**CONFIDENTIAL**

205724

Efficacy: Tables						
StInt No.	SAC No.	Population	IDSL / Example Shell	Title	Programming Notes	Deliverable [Priority]
2.14		PP		Analysis of Change from Baseline Monthly Mean E-RS: COPD Total Score up to Month 6 by Baseline E-RS: COPD Total Score (<10, >=10)	Frequentist MMRM Endpoints: E-RS: COPD total score	StInt
2.15	2.9	PP		Analysis of Change from Baseline Monthly Mean E-RS: COPD Total Score up to Month 6 by Smoking Status at Screening (Current, Former)	Frequentist MMRM Endpoints: E-RS: COPD total score	StInt, SAC
2.16		PP		Analysis of Change from Baseline Monthly Mean E-RS: COPD Total Score up to Month 6 by Country	Frequentist MMRM Endpoints: E-RS: COPD total score	StInt
2.17	2.10	PP		Analysis of Change from Baseline Monthly Mean E-RS: COPD Total Score up to Month 6 by % Predicted FEV1 at Screening (<50, >=50)	Frequentist MMRM Endpoints: E-RS: COPD total score	StInt, SAC
2.18	2.11	PP		Analysis of Change from Baseline Monthly Mean E-RS: COPD Total Score up to Month 6 by Baseline CAT Score (<10, >=10)	Frequentist MMRM Endpoints: E-RS: COPD total score	StInt, SAC
2.19		PP		Analysis of Change from Baseline Monthly Mean E-RS: COPD Total Score up to Month 6 by Exacerbation History (>=2 moderate/severe vs. 1 moderate/severe, prior year)	Frequentist MMRM Endpoints: E-RS: COPD total score	StInt
2.20		PP		Analysis of Change from Baseline Monthly Mean E-RS: COPD Total Score up to Month 6 by COPD Medication Grouping at Baseline (ICS+LABA+LAMA, ICS+LABA, LABA+LAMA, Other)	Frequentist MMRM Endpoints: E-RS: COPD total score	StInt

Efficacy: Tables						
StInt No.	SAC No.	Population	IDSL / Example Shell	Title	Programming Notes	Deliverable [Priority]
2.21		PP		Analysis of Change from Baseline Monthly Mean E-RS: COPD Total Score up to Month 6 by CMH Status at Baseline	Frequentist MMRM Endpoints: E-RS: COPD total score	StInt
2.22		PP		Analysis of Change from Baseline Monthly Mean E-RS: COPD Total Score up to Month 6 by Season	Frequentist MMRM Endpoints: E-RS: COPD total score	StInt
	2.12			Summary of Responders to E-RS: COPD Total Score, SGRQ and CAT at Month 6	Include categories for E-RS, SGRQ, CAT, E-RS+SGRQ, E-RS+CAT, SGRQ+CAT, E-RS+SGRQ+CAT, None, Missing	Post SAC
Exacerbations						
2.23	2.13	PP		Summary of On-treatment HCRU Exacerbations		StInt, SAC
	2.14	PP		Summary of On-treatment Details of Moderate/Severe HCRU Exacerbations		SAC

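### The mITT SAE and fatal-event tables can miss hospitalised or fatal COPD exacerbations recorded as disease-related events, and the SAP lists no by-arm table of all deaths

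*SAP*

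**What the plan says.** **Objective and population.** Protocol section 4 makes safety a primary objective: "To compare the safety of danirixin with placebo in participants with COPD". Its endpoint is adverse events, laboratory values, vital signs and ECG. Protocol 10.5.2 places all safety endpoints in the mITT population by treatment group. SAP section 8 defines the safety estimand over everyone randomised and dosed.

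**Routing of exacerbations.** Protocol 9.1.2 and 9.2.6 treat COPD exacerbations as DREs and keep them out of standard expedited SAE reporting even if they qualify as SAEs. Protocol 9.2.6 adds: "These events will be recorded on the DRE page". The event must be recorded as an SAE instead if the investigator finds it worse than expected for that participant, or sees a reasonable possibility that it is related to treatment. Appendix 4 says that an event which is not an AE cannot be an SAE, and gives as examples "hospitalization for signs/symptoms of the disease under study, death due to progression of disease".

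**Deaths.** Protocol 9.2.5 requires the Death section of the CRF for "all deaths, whether or not they are considered SAEs".

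**Displays.** In SAP 14.11.7, Tables 3.9 and 3.11 summarise on-treatment SAEs and Table 3.12 is "Summary of On-treatment Fatal Serious Adverse Events by [System Organ Class and] Preferred Term", all in mITT. Listing 19 lists fatal SAEs. SAP 14.6.3 defines the top exacerbation class as "Severe: required in-patient hospitalization, an emergency room visit, or resulted in death". These events are tabulated in SAP 14.11.5 under efficacy, in the per-protocol (PP) population: Table 2.13 ("Summary of On-treatment HCRU Exacerbations"), Table 2.14 (details of each moderate or severe event) and Table 2.18 (time to first severe event).

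**The concern.** Whether a hospitalised or fatal exacerbation reaches an mITT safety table depends on the investigator's view of what was to be expected for that participant, or of causality. Two similar events can therefore land in different datasets. The tables that do count severe exacerbations by arm use a population that does not match the safety estimand.

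The trial compares safety with placebo as a primary objective, names impaired host defence as a potential risk (Protocol 3.3.1) and has no independent data monitoring committee (Protocol 5.1). Protocol 9.4.5 itself notes that the features of pneumonia and of exacerbations overlap. If severe respiratory events were unevenly distributed across arms, the tables that a reader would consult first for serious and fatal events might not show it.

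**Working it through.** The documents state no expected number of SAEs, deaths or severe exacerbations, so there is no plan figure to reproduce. The check is to follow each kind of event through the final-analysis displays.

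| Event | mITT by-arm SAE or fatal-SAE table | PP by-arm exacerbation table | mITT listing |
|---|---|---|---|
| Exacerbation recorded as an SAE, onset on treatment | 3.9 and 3.11; 3.12 if fatal | not needed for this check | 19 if fatal |
| Severe or fatal exacerbation kept as a DRE, participant in PP, before any listed deviation | none | 2.13, 2.14; 2.18 if it is the first severe event | 48 |
| The same, participant outside PP or event after a listed deviation | none | none | 48 |
| Severe or fatal exacerbation kept as a DRE, onset more than 3 days after treatment stop | none | none (displays are on-treatment) | 48 |
| Fatal SAE, onset more than 3 days after treatment stop | not in 3.12 | none | 19 |

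The inputs to the table are:

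1. **On-treatment window.** SAP 14.4.1.3 ends it at treatment stop plus 3 days, by onset date. Follow-up runs up to 28 days after the last dose (Protocol Table 1). Table 3.5 summarises post-treatment AEs, but its title does not separate fatal ones.
2. **What PP removes.** SAP Appendix 1 excludes participants with any of six listed eligibility deviations. At the final analysis it also removes data from the time of a later listed deviation, including stopping study medication for more than 14 days. Protocol 9.1.2 allows treatment to be stopped in order to treat an exacerbation, and Protocol 8.1.4 gives hospitalisation for one as an example of a reason for interruption. Some of the lost data may therefore follow a severe event.
3. **Other displays.** Figure 1.1 (mITT) combines death with withdrawal. Table 1.31 (mITT) counts medications given for exacerbations, not the events. At the strategic interim, Table 2.25 used ITT, but it pooled moderate with severe events and is not a final-analysis table.

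**Scale, as an illustration only.** Person-years per arm at full exposure = (600/6) × (168 + 3)/365.25 = 46.8. If 10% leave, on average halfway through, this becomes 46.8 × 0.95 = 44.5. The documents give no severe-exacerbation rate. At assumed rates of 0.05, 0.1, 0.2 and 0.3 per person-year, 46.8 person-years give 2.3, 4.7, 9.4 and 14.0 severe exacerbations per arm.

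These are ceilings on what could fall outside the SAE tables, not estimates of it. The number outside = severe events × share that meets an SAE criterion × (1 − share caught by the exception). Neither share is given, so for each assumed rate the result runs from 0 to the figure shown. An emergency-room visit alone makes an exacerbation severe under SAP 14.6.3, whereas the hospitalisation criterion for an SAE in Appendix 4 requires inpatient admission.

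**The case against.** The strongest reply is that the separation is declared design and most events remain visible. Exacerbations are a prespecified secondary endpoint with their own by-arm analyses, and the severe class includes fatal events. Table 2.14 reports outcome and hospitalisation for each moderate or severe event. The Safety Review Team monitors DREs routinely. All diagnosed pneumonias, confirmed or not, must be reported as AEs or SAEs and are summarised in mITT (Tables 3.14 and 3.15), so the host-defence risk is largely covered without relying on the DRE exception.

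Much of this stands, and it rules out stronger readings that a reader might draw:

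- *That Table 3.12 is the only by-arm count of deaths.* Fatal exacerbations are counted by arm within the PP severe class. Whether the standard disposition shell behind Table 1.1 shows deaths cannot be checked, because shells are in a separate document.
- *That disease-related deaths and admissions are never SAEs.* Appendix 4 is conditional: the disease-under-study exclusion gives way when the event is more severe than expected. Protocol 9.2.6 makes SAE recording mandatory when either of its conditions is met.
- *That the safety comparison does undercount, by several events per arm.* That needs an assumed rate, no use of the exception, and emergency-room visits treated as SAEs.
- *That an interruption of more than 14 days deletes the exacerbation which caused it.* Data are dropped from the time medication stopped, and such an event would normally have begun earlier. Only later events are lost.

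None of this supplies a final mITT by-arm table of severe exacerbations or a listed table of all deaths. Routine review by the Safety Review Team does not create one either.

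**Conclusion.** The gap holds as a gap in the planned displays. Under the plan as written, a hospitalised or fatal exacerbation handled as a DRE appears in no mITT by-arm event table at the final analysis, only in Listing 48. The SAP lists no by-arm all-cause death table, although the data are collected for every death. Tables 3.9, 3.11 and 3.12 can therefore be incomplete for serious and fatal respiratory events, by an amount the documents do not allow to be estimated.

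The conclusion rests on the SAP's display list and titles, since the shells could not be seen. It does not show that any event will be missed or that the arms will differ. The change is worth making because safety is a primary objective, the PP tables do not serve the randomised-and-dosed estimand, and the remedy is small.

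There is also a wording conflict. Protocol 9.1.2 bases the worse-than-expected condition on intensity or duration, while 9.2.6 adds frequency. The wording affects which exacerbations become SAEs, so the two passages must be reconciled.

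**What to change.** In SAP 14.11.7:

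1. Add an mITT by-arm table of all-cause deaths from the Death CRF, on-treatment and through follow-up.
2. Add an mITT by-arm table of severe HCRU exacerbations, giving participants, events, hospitalised and fatal, without PP truncation.
3. Footnote Tables 3.9, 3.11 and 3.12 to say that exacerbations handled as DREs are not included.

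Reconcile the SAE-exception wording in Protocol 9.1.2 and 9.2.6. A combined table of participants with any SAE or any severe or fatal DRE is optional and not needed to close the gap.

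The cost is two summary tables and three footnotes. The Death CRF and the exacerbation page already hold the data, and no assessment or clinical rule changes.
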